**Method for measuring hip circumference**

The subject should wear non-restrictive briefs or thin bottoms. They should stand erect with hands held slightly away from the sides. The investigator should squat to the side of the subject and pass the measuring tape around the greater trochanter, without compressing the skin. The measurement is recorded to the nearest millimeter.

*7-2-2 Health status and dietary assessment*

**Dietary and nutritional status evaluation**

In order to assess the dietary habits of the volunteers two instruments will be applied, 24-hour recall questionnaire and a food frequency questionnaire. The 24-hour recall will be applied in the day on intervention (Day 3) to ensure compliance to the restricted diet on day 2. During the 24r-hour recall questionnaire volunteers will be asked about the amount and type of foods and beverages they consumed the day before.

The food frequency questionnaire (FFQ) is a self-administered questionnaire where the dietary habits of individuals for the past year are assessed using a food list and beverage items categorized in 22 categories. Usual frequency of consumption will be assessed for the 22 categories of foods. The objective is to get an overall estimation of the dietary pattern of the volunteer to identify dietary patterns far outside the standard dietary patterns observed in the French population.

*7-2-3. Metabolomics analysis*

Urine and Blood samples will be analyzed using a UPLC-QTOF-MS (Waters Corporation, Manchester, United Kingdom) platform for the detection of metabolites, equipped with an electrospray source and a lock mass sprayer to ensure accuracy. Later on, a small number of urine samples will be analyzed using a high resolution Thermo Scientific LTQ Orbitrap Velos hybrid mass spectrometer to obtain accurate masses and molecular formulas of potential biomarkers of intake. Several online chemical databases will be queried using the accurate formula or mass to search for possible hits of chemical structures and compounds.

GC-MS and NMR analyses of the samples will also be conducted in a collaborative research unit of the FoodBALL project, at the Max-Rübner Institute in Karlsruhe.

**8 – TRIAL TREATMENT, DOSAGE FORM, AND DOSAGE REGIMEN OF THE INVESTIGATIONAL PRODUCTS**

**8-1 INVESTIGATIONAL PRODUCT/TREATMENT**

Bananas and tomatoes will be bought in a local grocery. A unique dose of 240g banana and 300g tomatoes will be given to the volunteers.

The control drink will be **neutral flavored Fresubin® 2kcal fiber**. Volunteers will drink 250 mL on the Intervention 1 (volunteers only drink Fresubin® 2kcal fiber as a control) and 150 ml of Fresubin plus the test food of interest on Intervention 2 (Fresubin® 2kcal fiber plus 240g of banana) and Intervention 3 (Fresubin® 2kcal fiber plus 300g of tomatoes).

Nutritional composition of Fresubin® 2kcal fiber is as follows:

Nutritional Composition		Per 100ml	Per 200ml
Energy	kcal	200	400
Protein	g	10	20
Nitrogen	g	1.6	3.2
Carbohydrate	g	22.5	45
Of which sugars	g	3.2-5.8*	6.4-11.6

Of which lactose	g	≤0.3	≤0.6
Fat	g	7.8	15.6
Of which saturated fatty acids	g	0.6	1.2
Of which polyunsaturated fatty acids	g	1.4	2.8
Of which monounsaturated fatty acids	g	5.8	11.6
Fibre	g	0, 1.5-1.6 	0, 3.2 
Water	ml	69-70*	138-140*
Osmolarity	mosmol/l	495-650	
Osmolality	mosmol/kg H2O	720-950	

*Information obtained from: <http://www.fresenius-kabi.co.uk/4727.htm>*

## 9 – STATISTICAL ANALYSIS

Data will be collected in ad hoc developed databases and analyzed according to the classical workflow used for metabolomics data. Data will be cleaned in a standardized way. Univariate (ANOVA with Benjamini Hochberg correction) and multivariate analyses (Principal Component Analysis, Partial-Least-Square-Discriminant Analyses, and Hierarchical Clustering analysis) will be applied to pinpoint the detected metabolites which significantly vary along time after the intake of banana or tomato.

The statistical analysis will be centralized and performed by the INRA investigators, in close collaboration with the statistician of the Metabolomics platform ([name], PFEM: Plateforme d'Exploration du Métabolisme).

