### 5-2 SAMPLE SIZE CALCULATION

As untargeted metabolomics is a data driven approach, which consists in detecting thousands of metabolites in biological samples with various analytical and inter-individual variability, it is not relevant to calculate a unique statistical power to determine the number of subjects. Nevertheless, previous studies showed that metabolomics allows identification of food intake biomarkers in controlled intervention studies with 4 to 20 volunteers

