Projet BioBanaTom “Identification of new biomarkers of banana and tomato intake”

Protocol ID: 2016-A00153-48

Statistical Analysis for urinary and plasma metabolome changes

after banana and tomato intake

Version 2 – 25/06/2018

The statistical analysis is centralized and performed by the INRA investigators, in close collaboration with the statistician of the Metabolomics platform ([name] INRA, [name], PFEM: Plateforme d’Exploration du Métabolisme).

The dataset resulting for, the urine samples of the clinical trial, ion intensities is normalized according to the volume collected for each urine fraction. A PCA model is applied to the normalized dataset to detect possible outliers in the dataset. Q primary PLSDA model is built using the three interventions as “Y” variables. The dataset are also assessed separately for banana versus control and tomato versus control.

To better discriminate the ions according to the intake of banana, an OSC-PLSDA model is built with the dataset containing control and banana samples (n=24). Statistical analysis is performed with SIMCA-P+ software (version 14.0, Umetrics, Umea, Sweden). The OSC filter is built with log transformed and Pareto scaled data using treatment (banana vs control; tomato vs control) as correction factor. A k-fold cross validation method is used with 4 subsets to predict the ability of the model to correctly classify samples to the corresponding dietary treatment. Q^2 is used to assess the prediction power and to determine the reliability of the model a permutation test (n= 500) is carried out.

Simultaneously, the difference in intensity of the extracted features between dietary treatments is assessed by applying a Student T test with Benjamini Hochberg correction (BH) for multiple comparisons using Metaboanalyst 3.0 [20]. Significance level is established at p value BH <0.05. Those features with a variable importance of projection (VIP) higher than 2 in the OSC-PLS-DA model, a T-test with BH p value <0.05 and which present in higher intensity in the urinary samples of the banana group are prioritized for identification as candidate biomarkers of banana intake. The same strategy is applied for the tomato dataset.

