The dataset resulting from the analysis of plasma samples is assessed separately for banana and tomato versus control. Principal component analysis is performed for the detection of outliers in the dataset. For a first selection of ions, a one way ANOVA with a post hoc between the different time points is

applied using SPSS IBM version 22. Ions that were higher and significantly different than time point 00h (p value <0.01) are selected to be analyzed using a PLSDA model using SIMCA-P (version 14.0, Umetrics, Umea, Sweden). Ions with a VIP>2 and in higher intensity in banana or tomato are selected as plausible biomarkers of intake.

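### The protocol promises Benjamini-Hochberg correction for the ANOVA over time; the SAP's plasma ANOVA omits it, so the first plasma filter lacks the stated false discovery control

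*Protocol*

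**What the plan says.** Protocol section 9 names the univariate method as "Univariate (ANOVA with Benjamini Hochberg correction) and multivariate analyses". Its purpose is to "pinpoint the detected metabolites which significantly vary along time after the intake of banana or tomato". The section does not separate urine from blood and gives no level for the correction.

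The SAP treats the two fluids differently.

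- **Urine:** treatments are compared by "applying a Student T test with Benjamini Hochberg correction (BH) for multiple comparisons", and "Significance level is established at p value BH <0.05". This is a t test rather than an ANOVA, but it is corrected across features and the level is stated.
- **Plasma:** as a first selection, "a one way ANOVA with a post hoc between the different time points is" applied. Then "Ions that were higher and significantly different than time point 00h (p value <0.01) are selected" for the PLS-DA. Finally, "Ions with a VIP>2 and in higher intensity in banana or tomato are selected as plausible biomarkers of intake".

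The plasma paragraph does not mention BH, sets no threshold for the overall ANOVA and does not name the post hoc. Neither document says which prevails. Protocol section 11-9 requires protocol changes to be made by amendment, and nothing in the supplied text amends section 9 or explains why urine keeps BH and plasma does not.

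**The concern.** The ANOVA over time is the one analysis that both documents describe for blood. The protocol says its p values are corrected across metabolites; the SAP carries it out without that step. According to Protocol section 5-2, the approach "consists in detecting thousands of metabolites in biological samples", so correction across ions has a large effect on which ions are kept.

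The contrast with 00h is the only p-value threshold in the plasma selection. The VIP>2 rule that follows carries no error rate. VIP is also relative (squared VIPs average 1 over the ions entered), so chance ions that enter can shift the VIPs of the others. The SAP states cross-validation and a permutation test for the urine model but neither for plasma. A reader of the protocol would credit the plasma selection with false discovery control that the SAP does not provide.

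**Working it through.** The plan has no power or error-rate figure to reproduce: Protocol section 5-2 declines to calculate one. The check compares the texts and then sizes the missing step.

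**1. Which p value each rule uses.** For each ion, a one-way ANOVA over six times gives one overall p value and five contrasts against 00h. The protocol attaches BH to the ANOVA. The SAP attaches p<0.01 to a contrast. The defect is therefore an omitted step, together with a missing ANOVA threshold and an unnamed post hoc.

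**2. Inputs.**
- From the documents: 12 volunteers (Protocol section 4); blood at 0, 1, 2, 4, 6 and 24 h (section 6-3-1); p<0.01, higher than 00h (SAP).
- Assumed: 2,000 ions; independent normal errors; true ions raised 1.5 SD at two times; 1%, 2%, 5% or 20% of ions truly rising; BH level 0.05, borrowed from the SAP's urine rule because the protocol gives none.

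**3. Null ions that pass.** A two-sided p<0.01 counted only when upward is 0.005 per contrast. Over five independent contrasts the chance of at least one pass is 1 − 0.995^5 = 0.0248. Simulation with the shared 00h, unadjusted contrasts and 12 per time gives 0.0208. If the overall ANOVA must also reach p<0.01, it is 0.0033. With every ion null, 0.0208 × m is about 21, 42 and 104 ions for m = 1,000, 2,000 and 5,000.

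**4. False share at entry to the PLS-DA** = null ions passing / all ions passing. With unadjusted contrasts and no gate, 18.5 of 20 and 37.5 of 40 true ions pass:
- 1% true: 1,980 × 0.0208 = 41.2 null ions; 41.2 / (41.2 + 18.5) = 69%.
- 2% true: 1,960 × 0.0208 = 40.8 null ions; 40.8 / (40.8 + 37.5) = 52%.

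With the ANOVA gate, taking the same true ions to pass: 1,980 × 0.0033 is about 6.5, and 6.5 / 25.0 = 26%; 1,960 × 0.0033 is about 6.5, and 6.5 / 44.0 = 15%.

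**5. All rules, by simulation** (ranges span repeat runs):

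| Rule for entry to the PLS-DA | 1% true | 2% true | 5% true | 20% true |
|---|---|---|---|---|
| Unadjusted contrast, no gate | 68–69% | 51–52% | 29% | 8% |
| Dunnett, no gate | 38% | 23% | 10% | – |
| ANOVA p<0.01, then unadjusted contrast | 25–27% | 13–16% | 6–7% | 1–2% |
| Tukey, no gate | 20–21% | 11% | 4–5% | – |
| BH<0.05 on ANOVA, then unadjusted contrast | 1–3% | 1–3% | 1–3% | 1–2% |

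**6. Cost in true ions.** With BH first, 16.6–16.9 of 20 and 35.3–35.5 of 40 true ions pass. The loss is 18.5 − 16.9 = 1.6 up to 18.5 − 16.6 = 1.9 of 20, and about 2 of 40 (37.5 − 35.5).

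**7. Not covered.** The simulation stops at entry to the PLS-DA. It does not model VIP>2 or the requirement of higher intensity with the food.

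**The case against.** The strongest reply is that the two rules can coexist. BH on the overall ANOVA and p<0.01 on the contrast act on different p values, so the SAP could simply be giving the second stage. That is right as far as it goes. A reader might infer that the documents set two rival levels for one test and look for the share of ions at which the BH cut-off equals 0.01. The documents do not support that, because one ion's contrast p value cannot be judged against a BH cut-off meant for its ANOVA p value. What remains is that the SAP never states the first stage.

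Four further points limit the size.

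- The SAP does not call the plasma test uncorrected. That is inferred from the missing BH label, which the urine rule carries. An adjusted post hoc or an ANOVA gate would cut the false share considerably, as the table shows. Neither is a false discovery correction across ions.
- The protocol gives no BH level, so the difference cannot be fixed from the documents.
- Every arm includes 150–250 mL of a 2 kcal/mL drink (Protocol sections 6-1 and 8-1). Many plasma ions may truly rise from 00h, so 1–2% may be too low. At 20% the gated rule and BH pass nearly the same number of false ions (5.4 and 5.5 of 2,000).
- The step is called a first selection in a discovery study, and its output is only plausible biomarkers.

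All four stand as limits on size. None supplies the missing step.

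**Conclusion.** The inconsistency is real: the protocol promises BH for the ANOVA over time, and the SAP's only such ANOVA has none. The first plasma filter lacks the false discovery control stated in section 9.

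Its size is uncertain. Under the assumptions above, with 1–2% of ions truly rising, the false share at entry to the PLS-DA is about 11–26% under the milder readings (Tukey or gate), 23–38% with Dunnett, and about 52–68% under the harshest, against about 1–3% with BH first. At 20% true ions it is 8% with no gate and 1–2% with either the gate or BH.

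A reader might infer that half or more of the reported plasma biomarkers would be false. The documents do not support that: the high figures need an unadjusted, ungated post hoc and few responding ions, and they describe entry to the PLS-DA. The false share after VIP>2 and the food-direction filter has not been shown. The point should be corrected, but it does not undermine the study.

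**What to change.** In the SAP's plasma paragraph, apply BH over all plasma ions to the overall time-effect ANOVA p value and require BH p<0.05. Only then use a named post hoc comparison with 00h (p<0.01, upward) to choose ions and times. State the same level in protocol section 9.

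This takes one sentence in each document and one BH step on p values that the ANOVA already yields. In the example it loses about 1–2 of 20, or 2 of 40, true ions and removes about 40 false ones compared with the ungated, unadjusted rule. That cost assumes unadjusted contrasts after BH; an adjusted post hoc would cost more.

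If an uncorrected screen is intended, amend section 9 to say so, name the post hoc, and label the plasma filter as uncorrected in the SAP and in any report of the results.

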## 10 - BALANCE BENEFITS/RISKS

The risks involved in participating in this experiment are minimal. A venous puncture is comparable to a normal blood drawn and the only risk is that of a small local hematoma.

The inconveniences which can result of blood collection are possible infectious or inflammatory problems. These complications are exceptional and all the necessary measures of asepsis are taken to avoid them.

The food products that will be provided are commercially available products and for this reason do not bring any health risks.

## 11 – ETHICAL CONSIDERATIONS

### 11-1 INDEPENDENT ETHIC COMMITTEE

The protocol and the Subject informed form and consent will be submitted to The Independent Ethics Committee (CPP Sud-Est VI) and written approval from the Chair of the Ethics Committee is required before the initiation of the study.

The notification of the approval will be forwarded to the French authority ANSM. A request for authorization will be sent by the sponsor to ANSM before the start of the study.

### 11-2 REGULATION STATEMENT

The study will be performed in full accordance with the ethical principles stated in the Declaration of Helsinki 1964, as revised in 2008 (59th WMA General Assembly, Seoul, October 2008). The

participation of the subjects will be performed in accordance with the Code de la Santé Publique (National Health Codes), Law n°2004-806 of august 9th, 2004.

The clinical study will be conducted in compliance with the protocol, International Conference on Harmonisation (ICH), guidelines for Good Clinical Practice (GCP, as mentioned in the National Health Codes, article L.1121-3) and in the decree of the November 24th, 2006.

### **11-3 INSURANCE**

The sponsor, INRA has an insurance (N° 4623359604) which is in accordance with the legal requirements. This insurance provides cover for damage to research subjects through injury or death caused by the study product and/or study procedures.

It is to note that the non compliance with the legal requirements of the research (absence of CPP opinion, absence of ANSM's authorization, non consent of the person, the continuation of a suspended or speechless research) is an exclusion clause of the guarantee.

### **11-4 DOCUMENTATIONS OF THE RESEARCH**

Before starting the research, the investigator will supply to the sponsor a copy of his personal curriculum vitæ dated and signed and containing his number of registration in the Medical association, as well as all the investigators.

The version of the protocol accepted before submission with its appendices will be jointly signed by the investigator and the scientific in charge of the study.

For every new version of the protocol, (amendments and/or requests of the authorities), a new number and the date will be attributed and the same signatures will be collected.

The investigators agrees that the study is conducted in accordance with the Public Health law N° 2004-806 - 9 August 2004 on biomedical research, the implementing decree N° 2006-477 from 26/04/2006 amending chapter I of title II of book I of the first part of the code of Public Health relating to biomedical research and the applicable orders.

### **11-5 INFORMED CONSENT**

All the participants will give freely their written informed consent before their selection in the study. Prior to this, the investigator or his delegate had inform each participant of the objectives, benefits, risks and requirements imposed by the study, as well as the nature of the study products.

The participant will provided with an information and consent form in clear, simple language. Two original information and consent forms will be completed, signed and dated personally by the participant and by the investigator or co-investigator for collecting the informed consent. The participant will be given one signed original information and consent form, the second original will be kept by the investigator and archived during, at least, 15 years.

### **11-6 ASSESSMENT OF SAFETY**

#### *11-6-1 Definitions*

#### -ADVERSE EVENT (AE)

AE is any untoward medical occurrence in a patient or clinical investigation subject administered a study product and which does not necessarily have a causal relationship with the study product (derived from the ICH-GCP definition).

#### -SERIOUS ADVERSE EVENT (SEA)

SAE is any untoward medical occurrence that at any dose:

- results in death,

- is life-threatening (at the time of the event),
  - requires inpatient hospitalisation or prolongation of existing hospitalisation,
  - results in persistent or significant disability or incapacity,
- or
- is a congenital anomaly or birth defect

#### -SUSPECTED UNEXPECTED SERIOUS ADVERSE REACTION (SUSAR)

A SUSAR is both:

- an SAE that is judged to be at least possibly related to the study product by the either investigator or sponsor, and
- unexpected (not listed in the Product Information Brochure)

#### *11-6-2 (Serious) Adverse events handling*

#### -(S)AE RECORDING

Any (S)AE as reported spontaneously by the subject or observed by the investigator or staff, is recorded on the AE form during the course of the study. The investigator must ensure that all required information is captured on this form, including the nature, onset, duration, and severity of the event, the relationship to the study product, and the action taken.

Only untoward medical events occurring after first study product intake are recorded as (S)AE (Events occurring during the Baseline period and/or before first study product intake are recorded as pre-existing condition on the Relevant Medical History and Pre-Existing Conditions page in the CRF).

When a subject undergoes a medical intervention or hospitalisation in absence of an Adverse Event (such as treatment for a pre-existing condition or hospitalisation for elective surgery or diagnosis), this intervention/hospitalisation must be reported on the AE page and not as SAE. These procedures will be handled like AEs, and timelines for reporting are the same as for reporting AEs. Complications or prolongations of hospitalisation that result from such procedures must be reported as (S)AEs, according to the applicable reporting timelines and procedures.

The severity of any (S)AE is scored as follows:

- Mild: transient or mild discomfort; no medical intervention/therapy required
- Moderate: mild to moderate limitation in activity; some assistance may be needed; and/or minimal medical intervention/therapy required
- Severe: marked limitation in activity; some assistance usually required; and/or significant medical intervention/therapy/hospitalisation required

The relationship of the (S)AE to the study product is assessed as being not related / unlikely related / possibly related / probably related / definitely related.

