## SUMMARY

Promotor	INRA
Main investigator	[name]
Co-Investigators	[name], [name], [name]
Title	Identification of new biomarkers of banana and tomato intake
Rational	In epidemiological studies, dietary intakes are assessed by questionnaires, an approach with inherent limitations associated with self-reporting : memory bias, difficulty to estimate portion size, insufficient coverage of the dietary diversity... The use of biomarkers of food intake should markedly improve the accuracy of dietary assessment, However, only few validated biomarkers are available. A large European project (FoodBALL) was funded by the JPI HDHL to identify a large range of new biomarkers of intakes, using untargeted metabolomics on urine and plasma samples collected in a series of controlled nutritional intervention studies.
Objective	The BioBanaTom study aims, in the framework of the FoodBALL project, at identifying new biomarkers of intake for banana and tomato, two important foods of the European diet.
Evaluation criteria	Main Criteria: Identification using metabolomics of plasma and urine metabolites specifically associated to banana and tomato intake, for validation as biomarkers. Secondary criteria : Obtention of reference metabolomics profiles which may be related to metabolic impact of an acute intake of tomato or banana.
Methodology	Cross-over randomized, open, controlled
Number of subjects	12
Undesirable effects	No undesirable effect expected beyond those link to blood sampling (small local hematoma, slight local inflammation)
Recruitment modalities	Volunteer file of UEN declared to the CNIL, mailing CHRU and INRA Clermont-Ferrand-Theix, local medias. The selection of the volunteers will be performed during medical inclusion visits.
Main selection criteria	Inclusion criteria Men and women, healthy (normal medical and biological exam), non-smoking, aged 18 to 40, BMI>18,5 and <30 kg/m  , with no aversion for banana or tomato. Exclusion criteria Smokers, diagnosed with infectious or chronic disease, under medication (except contraception pill), having followed an antibiotic treatment in the last 3 months, consuming dietary supplements several times a week, pregnant and lactating women, vegetarian as the protocol implies consumption of standardized meal containing meat.

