## 6 – DESIGN OF TRIAL TO BE CONDUCTED

### 6-1 STUDY PROCEDURES

All the participants will give freely their written informed consent before their selection in the study. The investigator or co-investigator will collect written consent from each participant before, or at the latest on, the day of the first study visit. Prior to this, the investigator or his delegate will inform each participant of the objectives, benefits, risks and requirements imposed by the study, as well as the nature of the study products.

The participant will receive an information and consent form in clear, simple language. He will be allowed ample time to inquire about details of the study and to decide whether or not to participate in the study.

Subjects will come to the Investigational Site for screening to determine whether they are eligible to participate in the study. Information on demographics, anthropometrics, vital signs, relevant medical history and concomitant medication and nutritional supplements (including vitamins) will be collected. A blood sample will be collected to measure: full blood count, platelets, CRP (C Reactive Protein), glycemia, ionogramme (Na+, K+, Cl), hepatic, lipid and renal profile. A total volume of 10ml will be collected to perform this biological test. All inclusion and exclusion criteria will be checked by the investigator or co-investigator. Subjects will also complete a food frequency questionnaire (Appendix 2).

Selected subjects will be definitively included after validation of their biological test by the investigators. Subjects will be personally informed by the medical doctor in case of non inclusion if their biological test presents anomalies. Results will be delivered to them confidentially. Their medical doctor will be informed with a letter from the investigator. The results of biological tests will be kept in the envelope dedicated to each volunteer for this study and only people involved in the research will have access to documents (Nurses, co-investigators, dieticians, Clinical Research Assistant) in accordance with Good Clinical Practices.

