In the morning of Day 3, subjects will arrive fasted at Investigational Site at around 7.30 am. As stated previously volunteers will be assigned randomly to one of the three interventions, Fresubin ® 2kcal fiber, 240g of banana plus control drink, or 300g of tomato plus control drink. Throughout the intervention, subjects will have free access to water, maximum 250ml of water per hour until 6 hours after intervention (1.5L in total).

A trained phlebotomist will place a catheter on the subject's arm before the intake of the test foods to collect the baseline sample. Then four other samples will be collected postprandially after **1h, 2h, 4h, and 6h**.

A total of **7 urine samples** will be collected. The first void of urine will be collected by the subjects at home upon the morning of Day 3 and the rest of the samples after the intake of the test foods as follows: **0-1h, 1h-2h, 2h-4h, 4h-6h**. The urine samples corresponding to **6h-12h** and **12-24h** interval will be collected by volunteers at home until the morning of **Day 4**. Urine samples will be kept at 4°C between collections; the use of preservatives will not be needed.

After the 6h collection of blood, the peripheral catheter will be removed and subjects will have lunch composed of rice and chicken meal, then subjects will be allowed to go home. Before leaving the Investigation center, participants will be instructed to prepare a standardized dinner based on chicken and rice. Volunteers will not be allowed to eat or drink anything except water and the standardized dinner.

On the morning of **Day 4**, subjects will arrive fasted at the investigation center at around 7.30 am in order to collect the **24h** blood sample and will deliver the **6h-12h** and **12-24h** urine collection. Afterwards participants will receive a breakfast (free composition) on site and be allowed to follow their normal diet until the run in phase of the following intervention period initiates. This procedure will be repeated for each intervention (1,2,3) separated by a minimum 3 day period (=7 days between visits).

*Table 1. Summary of trial procedures*

	Who	Where
Day 1: Run in		
Restricted diet: no banana or tomato intake	Volunteer	At home
Day 2: Run in		
Restricted diet: no intake of tomato, banana, tea, coffee, wine, fruit juices, plant foods. Dinner based on chicken and rice,	Volunteer	At home

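### Adverse-event recording opens at first food intake, so blood-sampling harm that appears earlier is labelled pre-existing and bypasses SAE reporting

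*Protocol*

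**What the plan says.** Section 11-6-2 of the protocol opens broadly: any (S)AE that is reported or observed "is recorded on the AE form during the course of the study". The next paragraph narrows this: "Only untoward medical events occurring after first study product intake are recorded as (S)AE". Events in the baseline period or "before first study product intake are recorded as pre-existing condition on the Relevant Medical History and Pre-Existing Conditions page in the CRF".

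The AE definition in section 11-6-1 is tied to the product in the same way: "AE is any untoward medical occurrence in a patient or clinical investigation subject administered a study product". So is causality in section 11-6-2: "The relationship of the (S)AE to the study product is assessed as being not related", and so on up to definitely related. There is no grade for relationship to a study procedure.

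On where risk comes from, the Summary says: "No undesirable effect expected beyond those link to blood sampling". Section 10 names a small haematoma from venous puncture and, exceptionally, infection or inflammation from blood collection. It attributes no health risk to the foods.

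On timing, section 6-1 places a blood draw at screening: "A total volume of 10ml will be collected to perform this biological test". On the first Day 3 the catheter goes in "before the intake of the test foods to collect the baseline sample".

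**The concern.** The recording window is tied to the exposure that the protocol regards as harmless, not to the procedures that it regards as carrying the risk. Part of that risk is taken before the window opens. An event caused by the study in that interval must be entered as something the volunteer already had, which is wrong as a description. It also takes the event off the formal safety routes in section 11-6-2: the investigator's SAE report within 48 hours, and the sponsor's SAE listing to the ethics committee.

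The causality scale has a related gap that applies throughout the study. A catheter-site infection after intake is recorded, but it can be graded only against the food. A correct grade of not related would then hide that the study caused it. Section 11-3 states that the insurance covers injury from study procedures as well as from the product, so the protocol itself accepts that procedures can cause harm.

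**Working it through.** **Blood volume, as a check that the procedures are counted correctly.** Section 6-3-1 gives 8 mL at 6 time points in 3 periods, plus 10 mL at screening: 8 × 6 × 3 + 10 = 144 + 10 = 154 mL. This reproduces the protocol's total.

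**Order of procedures.** Table 2 puts the screening visit before the first Day 1. Two run-in days come before the first Day 3. Table 1 orders Day 3 as catheter, baseline sample, then test food. Section 6-1 has the catheter removed after the 6 h sample.

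**Venous accesses per volunteer.** 1 screening draw + 3 catheters + 3 Day 4 draws = 7. The protocol does not say how the Day 4 sample is drawn. Because the catheter is out after 6 h, I assume a new puncture each time.

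**Procedures before first intake, per included volunteer.**
- Accesses: screening draw and first catheter, 2/7 = 28.6% (24 of 84 over 12 volunteers).
- Blood samples: 2 of 1 + 18 = 19, or 10.5%.
- Blood volume: 10 + 8 = 18 of 154 mL, or 11.7%.

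**Where an event would be filed.** The rule sorts by when the event occurs, not by when the needle went in.

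| Source of harm | Appears before first intake | Appears after first intake |
|---|---|---|
| Screening draw | History page, as pre-existing | AE form |
| First catheter placement and baseline sample | History page, as pre-existing | AE form |
| Later samples from the first catheter, and its removal | Cannot occur | AE form |
| Second and third catheters, all Day 4 draws | Cannot occur | AE form |

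The two misfiled cells differ in practice. The screening draw is followed by at least the two run-in days, which leaves time for a local reaction to show before intake. The first catheter stays in place until after the 6 h sample, so only harm visible between placement and eating is affected. The documents do not give the length of that interval.

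**Volunteers who fail screening.** Their only study puncture is the screening draw, and they never reach a product intake. No harm from it can become an (S)AE under the rule.

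**The case against.** The strongest reply is that little is lost, and much of it is right.

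- *The first catheter is mostly covered.* A reader might infer that all harm from it is filed as pre-existing. The text does not support that: anything that appears after intake is recordable.
- *The 29% is not missed harm.* A reader might take 2 of 7 as the proportion of events lost. It counts procedures only. Just 1 of 7 accesses (14.3%), the screening draw, lies well clear of the window, and even its late effects are recordable after intake.
- *The sponsor is not blind.* A reader might infer that these events never reach the sponsor or the ethics committee. Section 11-7 has the sponsor collect the original CRFs, which include the history page. Section 5-4 requires immediate notice of withdrawals, with reasons. Section 11-6-3 obliges the sponsor to tell the committee of anything that may worsen burden or risk, with no limit tied to intake.
- *Hospitalisation has a route.* Section 11-6-2 sends hospitalisation for a pre-existing condition to the AE page, and complications of it to (S)AE reporting. This helps only in part: the same sentence says that such an admission is not to be reported as an SAE.
- *The window agrees with the protocol's own AE definition.* So this is a design choice, not an internal contradiction.
- *The expected events are minor.* There are 12 healthy volunteers, safety is not an endpoint in section 7-1, and the nature of a puncture-site event often shows its cause.

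These points limit the size of the problem. They do not remove the mislabelling, which the rule requires, and none of the other routes ensures that the event is identified as caused by the study.

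**Conclusion.** The point holds in a limited form. Harm from the screening draw, or from the first catheter placement and baseline sample, that appears before first intake is classified as pre-existing. It is therefore outside the 48-hour SAE report and the SAE listing to the ethics committee. The exposure is 2 of about 7 venous accesses per volunteer, on the assumption of a new puncture for each Day 4 draw, and the whole exposure of those who fail screening. The documents give no event rates, so the number of events affected cannot be estimated; given the harms the protocol names, it is likely to be small.

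The weight is modest, since no biomarker comparison depends on it. The change is still worth making, because it concerns the accuracy of volunteer safety records and costs very little.

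**What to change.** - In section 11-6-2, start (S)AE recording at the first study procedure after consent, which is the screening blood draw.
- In section 11-6-1, align the AE definition so that it also covers events in consented volunteers after a study procedure, with or without product intake.
- Keep on the medical-history page only conditions present before consent.
- Add *relationship to study procedure* to the AE form, beside relationship to study product.

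The cost is a short text change in two sections, one form field, and a few more minor events to record, including some in volunteers who are screened but not included. The design, sampling schedule and analysis are untouched.
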